6.1.4. Discussion of the clinical investigation design

Up to 130 subjects will be enrolled in total; up to 80 healthy volunteers will be enrolled in part A and up to 50 with a stoma will be enrolled in part B.

To be included in the investigation, the subjects must comply with the selection criteria described in section 6.1.5 and must not comply with criteria described 6.1.5.

6.1.5. Inclusion and Exclusion criteria for subject selection and justification

Subjects interested in participating in the clinical investigation must comply with the following criteria:

Part A:

Inclusion criteria:

- 1. Have given written informed consent
- 2. Be at least 18 years of age and have full legal capacity
- 3. Have intact skin on the area used in the investigation

Exclusion criteria

- 5. Currently receiving or have within the past 2 months received radio- and/or chemotherapy
- 6. Currently receiving or have within the past months received topical steroid treatment in the abdominal skin area or systemic steroid (tablet/injection) treatment.
- 7. Are pregnant or breastfeeding
- 8. Have dermatological problems in the abdominal area (assessed by investigator)

Part B

Inclusion criteria:

- 1. Have given written informed consent
- 2. Be at least 18 years of age and have full legal capacity
- 3. Have had a stoma for more than one year
- 4. Has an ostomy with a diameter up to 35 mm
- 5. Have intact skin on the area used in the investigation

Exclusion criteria

- 1. Currently receiving or have within the past 2 months received radio- and/or chemotherapy
- 2. Currently receiving or have within the past month received topical steroid treatment in the peristomal skin area or systemic steroid (tablet/injection) treatment.
- 3. Are pregnant or breastfeeding
- 4. Have dermatological problems in the area used in the investigation (assessed by investigator)

Part A

Justification for inclusion criteria:

- 1. To meet the Helsinki Declaration
- 2. To meet the Helsinki Declaration
- 3. The adhesive strips must be applied on intact skin

Justification for exclusion criteria:

- 1. The skin undergoes major changes as a consequence of radio- and/or chemotherapy, and therefore it can be more fragile
- 2. Steroid product may interfere with the study endpoints by making the abdominal skin thinner and more fragile
- 3. Even though the ingredients and the recipes have been approved for human beings, their effect on embryos, foetuses and infants are unknown
- 4. The skin has to be intact in order to see a potential damage of the skin with the simulated output

Part B

Justification for inclusion criteria:

- 1. To meet the Helsinki Declaration
- 2. To meet the Helsinki Declaration
- 3. To ensure subjects are recovered from ostomy surgery
- 4. To be able to have adhesive strips applied to the peristomal area
- 5. The adhesive strips must be applied on intact skin

Justification for exclusion criteria:

[figure not shown]
- 1. The skin undergoes major changes as a consequence of radio- and/or chemotherapy, and therefore it can be more fragile to baseplate changes
- 2. Steroid product may interfere with the investigational endpoints by making the peristomal skin thinner and more fragile

- 3. Even though the ingredients and the recipes have been approved for human beings, their effect on embryos, foetuses and infants are unknown
- 4. The skin has to be intact in order to see a potential damage of the skin with simulated /real output
- 5. Other interventional investigation guidelines/products may interfere with these investigational endpoints.

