6.1. General

The investigation is open-labelled and is divided into two parts: Part A evaluates the adhesive strips on abdominal skin in healthy volunteers while part B evaluates the adhesive strips on peristomal and abdominal skin in people with a stoma.

Part A:

Investigation of adhesive strips will be performed in cohorts of minimum 4 and up to 80 subjects. Each cohort consist of 1 or more test visits and a compliance visit. The purpose of the investigation for the individual cohorts will be described in a sub-investigation document.

At each of the test visits, subjects have a maximum of six adhesive strips placed on the skin as illustrated in Figure 1. The adhesive strips are placed on either dry skin or skin wetted by buffer or simulated output. The adhesive strips can be removed at different time slots but after 72 hours at the latest (e.g. after 10, 60 minutes and 24 hours) or within the same time slot.

The ordering of the timeslots position (T1, T2 and T3) from belly - button will be randomized within each cohort if applicable.

Subjects can be asked to take a shower or ride an exercise bicycle for max 1 hour before application of adhesive strips or during wear.

Subjects can also be asked to apply and change adhesive strips every 24 hours between visits but for a maximum of 10 days between two visits. The strips should be applied at the same place every time

Each adhesive strip will be evaluated in a cohort of minimum 4 subjects and up to 80 subjects are enrolled and can test maximum 30 different types of adhesive strips.

Example illustrating test of adhesive strips. T1, T2 and T3 indicates different time slots for removing adhesive strips e.g. 10, 60 minutes and 24 hours:

[figure not shown]

Figure 1

Part B:

At each of the test visits, subjects have a maximum of four adhesive strips placed on the skin as illustrated in the Figure 2. The adhesive strips are placed on either dry skin or skin wetted by buffer, real or simulated output. The adhesive strips will be removed at different time slots but after 72 hours at the latest.

Subjects can be asked to take a shower or ride an exercise bicycle for max 1 hour before application of adhesive strips or during wear.

Subjects can also be asked to apply and change adhesive strips in the abdominal area every 24 hours between visits but for a maximum of 10 days between two visits. The strips should be applied at the same place every time.

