6.1.3. Rationale for the selection and measurement of end points

Peel force: Peel force is a very frequently used and relevant method for recording adhesive properties of new developed skin adhesives. It describes how good the adhesives stick to the skin. [2, 3]. Peel force is measured by peeling the adhesive strips from the skin surface

Adherent area: After peeling the adhesive strips from the skin surface a picture of the adhesives is taken. Based on visual inspection from the picture, the area not affected by water or output is considered the adherent area, which is a measurement for adhesives ability to resist moisture and output. The adherent area is measured by a ruler/ordinal 5-point scale.

Swelling of adhesives strips: The swelling of the adhesive strips measured by the difference in weight before and after test is an indicator of the ability of the amount of moist that the adhesive strips can absorb.

Trans Epidermal Water Loss (TEWL): TEWL is a standardized non-invasively method for describing the barrier function of the skin [1]. Damage to the skin surface (stratum corneum) will lower the barrier of the skin and thereby increase the water loss. This can be used as a proxy for the damaging effects of the adhesive.

TEWL is measured by applying a probe to the surface of the skin. The instrument is a Dermalab (Cortex Technology A/S, Hadsund).

Skin Conductance and Capacitance (hydration): Conductance and Capacitance is standardized non-invasively methods for measuring the hydration of the skin [1]. Both the conductance and capacitance is proportional to the skins hydration state and how the skin is influenced by adhesives. The capacitance measurement can measure deeper in the skin whereas the conductance measures in the top layer of the skin. Both measurements are done by applying a probe to the surface of the skin. The instruments is either a DermaLab (conductance, Cortex Technology A/S, Hadsund) or a MoistureMeterD (capacitance, Delphin Technology).

Occurrence of erythema: A change in the surface skin color is known to be related to a change in the blood flow. This can be measured non-invasively with a spectrophotometric instrument (Dermaspectrophotometer, Cortex Technology A/S, Hadsund) where both the redness and the color of the skin are measured.

pH: How the skin PH is influenced by adhesives. (applying a probe to the surface of the skin)

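### Neither part excludes people with a known allergy to skin adhesives or strip ingredients, and nothing requires anyone to ask before exposure

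*Combined protocol and SAP*

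**What the plan says.** The synopsis and section 6.1.5 each give four exclusions per part: recent radio- or chemotherapy, steroid treatment, pregnancy or breastfeeding, and a dermatological criterion. The last reads "Have dermatological problems in the abdominal area (assessed by investigator") in Part A and "Have dermatological problems in the area used in the investigation (assessed by investigator") in Part B. Its stated reason in Part A is "The skin has to be intact in order to see a potential damage of the skin with the simulated output"; Part B gives the same reason for simulated or real output.

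The only eligibility text that mentions the strips' ingredients justifies the pregnancy and breastfeeding exclusion: "Even though the ingredients and the recipes have been approved for human beings, their effect on embryos, foetuses and infants are unknown".

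On exposure, section 6.1 says of Part A that "subjects have a maximum of six adhesive strips placed on the skin" at each test visit. The Part B maximum is four. Strips come off after 72 hours at the latest. Section 6.1 also provides for daily changes by the subjects themselves: "Subjects can also be asked to apply and change adhesive strips every 24 hours between visits but for a maximum of 10 days between two" (the last words refer to test visits). The site stays the same each time; in Part B this applies to the abdominal area only. Section 6.2.1 allows up to 25 test visits per subject.

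On interpretation, section 6.1.3 says of a rise in TEWL: "This can be used as a proxy for the damaging effects of the adhesive". Erythema is justified by "A change in the surface skin color is known to be related to a change in the blood flow". The discomfort questions in section 6.1.2 ask about redness, itching or burning, and weeping, among other things.

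**The concern.** The exclusions are meant to keep out skin that is fragile or would disturb the endpoints; the steroid exclusion is justified in exactly those terms. In a study that repeatedly sticks experimental adhesives to skin, a known allergy to the material is at least as direct a threat, yet it is not named. Section 6.2.3 also states that no foreseeable factor could compromise the results.

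Safety is the main issue. Section 4.1 offers subjects no immediate benefit, and section 4.2 treats the employees in Part A as a vulnerable group. A risk that one question would reveal is hard to justify in that setting.

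Interpretation is a secondary issue. TEWL, erythema and discomfort would all be expected to rise in a subject who reacts. Section 7 has no rule for flagging or separating such a subject in the cohort summaries, and those summaries guide which adhesives are developed next.

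**Working it through.** The plan states no figure on this point, so the check is mainly textual, with short arithmetic on size.

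**Step 1. Test a hypothetical person against the criteria.** Take an adult with a known allergy to a skin adhesive, no current skin problem in the test area and none of the other exclusions. For Part B, add a stoma that meets the entry criteria.

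| Criterion | Result |
|---|---|
| Consent, age and legal capacity | met |
| Intact skin in the area used | met |
| Stoma duration and diameter (Part B) | met |
| Radio-/chemotherapy, steroids, pregnancy or breastfeeding | not excluded |
| Dermatological problems in the area | not excluded: the wording concerns the test area, and the reason given is intact skin at the start |

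The person is eligible in both parts as written.

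**Step 2. Look for the question elsewhere.** Baseline data in section 6.1.2 are age, gender, height and weight, and consent, plus stoma history, leakage and product experience in Part B. Allergy history is absent. The inclusion visit in section 6.2.1 does not mention it. Table 2 in section 14.1.2 lists peristomal skin irritation and mechanical trauma as anticipated effects, but not allergic reaction.

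**Step 3. Weight of one reactor in a cohort mean.** Inputs: minimum cohort 4 (section 7.2) and maximum Part A cohort 80 (section 6.1). With n subjects, one person carries 1/n of the mean: 1/4 = 25%, or 1/80 = 1.25%.

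Suppose the others change by 1 unit and the reactor by k units. The mean is (n − 1 + k)/n, so it rises by (k − 1)/n. The documents give no value for k; I assume 3 to 5.

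- n = 4: 2/4 to 4/4, a rise of 50% to 100%
- n = 8: 25% to 50%
- n = 20: 10% to 20%
- n = 80: 2.5% to 5%

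The effect is material only in small cohorts.

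**Step 4. Chance of enrolling such a person.** The documents give no prevalence. For an assumed prevalence p and independent subjects, P(at least one) = 1 − (1 − p)^n.

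| Assumed p | n = 4 | n = 50 (Part B maximum) | n = 80 (Part A maximum) |
|---|---|---|---|
| 1% | 3.9% | 39.5% | 55.2% |
| 2% | 7.8% | 63.6% | 80.1% |
| 5% | 18.5% | 92.3% | 98.3% |
| 10% | 34.4% | 99.5% | >99.9% |

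People who know they are allergic may not volunteer, which would lower these figures. The omission itself does not depend on them.

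**The case against.** The case on the other side has real force.

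- **The safeguards are not purely reactive.** A reader might infer that nothing can happen until a reaction has occurred. Section 6.1.7 does not support that: the investigator may withdraw a subject at any time in the subject's interest, and a disclosed allergy would be enough. Table 1 also repeats the eligibility check at visits 1 to 25. This stands, but it is discretion. Nothing prompts the question, and the repeated check tests criteria that do not mention allergy.
- **The maximum exposure is not a realistic one.** The ceiling for one Part A subject is 25 × 6 = 150 strip applications at visits. It would be wrong to read this as the expected exposure of someone who reacts. Section 6.1.7 requires withdrawal when safety or well-being is compromised, and section 6.2.1 requires skin complications to be evaluated before the subject continues.
- **A reaction would probably be seen.** Sections 7.1 and 7.3 provide for listings as well as summaries, and an outlier in a listing of four subjects is hard to miss. Adverse events are captured throughout, and section 14.1.2 treats redness of abnormal intensity or duration as an adverse device effect. This largely stands. What remains is that no rule says how such a subject is handled in the cohort summary.
- **The design limits the distortion.** Where one subject wears several adhesives, a reaction to a shared component raises several strips together and disturbs contrasts between them less than it disturbs a cohort mean. A reaction to one adhesive only is arguably information about that adhesive.
- **Part B has a partial screen.** Its subjects have had a stoma for more than one year and must have intact skin in the test area. Section 3 describes ostomy baseplates as adhesive products, so marked intolerance to those adhesives is less likely. This does not cover new ingredients, and it does not help Part A.

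**Conclusion.** The omission is confirmed in both parts, in the synopsis and in section 6.1.5. A person with a known allergy and clear skin is eligible for repeated strips, and no procedure requires the question beforehand. This is mainly an avoidable safety risk, reduced but not removed by investigator discretion.

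The effect on results is secondary. In a cohort of four, one reactor carries 25% of the mean of TEWL, erythema or discomfort; the 50% to 100% rise rests on the assumed threefold to fivefold response. A reader might go further and conclude that an allergic reaction would be mistaken for adhesive damage and would bias the trial. The documents do not support that. Individual data are listed, reactions are recorded as adverse events, and the primary endpoint in section 6.1.1 is strip weight, which is not directly affected. The study is exploratory, with no success criteria (section 7.4).

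This is a cheap improvement, not a flaw that undermines the study.

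**What to change.** Add one exclusion criterion to both parts, in the synopsis and in section 6.1.5: *Known allergy or hypersensitivity to any ingredient of the adhesive strips, the buffer or the simulated output.* Add a matching justification: a reaction could harm the subject and disturb the skin endpoints. Ask it at the inclusion visit, and again when a cohort introduces a new adhesive, using the eligibility check already scheduled in Table 1.

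The cost is one criterion and one interview question, with no test or extra visit. A few subjects will be lost, and the skin results will apply to people without known adhesive allergy. Section 6.1.7 already ties withdrawal to the selection criteria, so the sponsor should note that the new criterion would also apply to an allergy that becomes known during the study.

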1.2 Investigators

PRINCIPAL INVESTIGATOR & MEDICAL ADVISOR	INVESTIGATOR REPRESENTATIVE

2. Identification and description of the investigational material

The study includes a range of different adhesive strips with different water absorption properties.

Adhesive strips are not considered medical devices and therefore, approval of the clinical investigation from the competent authorities is not deemed necessary.

3. Justification for conducting the clinical investigation

The adhesives in the ostomy baseplates are developed to make the ostomy product seal to the skin and thereby minimise the risk of leakage episodes.

The purpose of the study is to investigate and understand how different water absorption properties in adhesives affect the initial adhesion and the adhesion during use to human skin.

The data from the investigation will be used to optimize the water absorption properties in adhesives to be implemented in future ostomy products.

Furthermore, data from abdominal skin and peristomal skin are compared to explore the resemblance between the two skin types. This will provide valuable knowledge for the development of ostomy products/adhesives and may minimize the number of clinical studies in ostomy users in the early development phase.

4. Ethical considerations, investigational material and clinical investigation risks and benefits

The clinical investigation is conducted in accordance with current law and applicable standards see section 12.

The rights, safety and well-being of human subjects shall prevail over interest of science and society.

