5.1. Objectives

The primary objective is to investigate water absorption in different adhesives.

Secondary objectives are

- To investigate the impact that different water absorption properties in adhesives have on the initial adhesion, adherent area and skin when applied to skin exposed to buffer, output (simulated in part A and real/simulated output in part B of the study) as well as to dry skin.
- To investigate the impact that different water absorption properties in adhesives have on the adhesion during use with and without conducting exercise (part A and B).
- To explore the variations of adhesive properties when applied to peristomal skin and abdominal skin (part B)
- To explore the variations in water loss and hydration between peristomal skin and abdominal skin (part B)

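### Part B's topical-steroid exclusion covers only peristomal skin, although Part B also tests abdominal skin and compares the two sites, so recent steroid use on the abdominal test area can bias that exploratory comparison

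*Combined protocol and SAP*

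**What the plan says.** **Sites tested.** Section 6.1 states that "part B evaluates the adhesive strips on peristomal and abdominal skin in people with a stoma".

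**Purpose.** Two of the four secondary objectives in section 5.1 are Part B comparisons of the sites, one for adhesive properties and one for water loss and hydration. Section 3 adds that "data from abdominal skin and peristomal skin are compared to explore the resemblance between the two skin types", and expects this knowledge possibly to reduce the number of early-phase studies needed in ostomy users.

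**Part B exclusion 2** (synopsis and section 6.1.5): "Currently receiving or have within the past month received topical steroid treatment in the peristomal skin area or systemic steroid (tablet/injection) treatment". The justification in section 6.1.5 is "Steroid product may interfere with the investigational endpoints by making the peristomal skin thinner and more fragile".

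**Part A exclusion on steroids** (section 6.1.5): the scope is "topical steroid treatment in the abdominal skin area or systemic steroid (tablet/injection) treatment". The justification is "Steroid product may interfere with the study endpoints by making the abdominal skin thinner and more fragile".

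**Neighbouring Part B criteria.** Inclusion 5 (intact skin) and exclusion 4 (dermatological problems, judged by the investigator) are worded to cover whatever skin area is tested. Exclusion 2 is not.

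**The concern.** By the plan's own reasoning, topical steroid can alter the endpoints on abdominal skin. Part A acts on that reasoning. Part B uses abdominal skin as one of its two test sites but screens only the other site for recent topical steroid.

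Recent exposure is therefore permitted on one side of a within-study comparison and barred on the other. If exposed subjects take part, the observed peristomal-versus-abdominal difference mixes the contrast between skin types with a steroid effect on the abdominal side. At stake is how the resemblance of the two skin types is interpreted. That resemblance is what the sponsor hopes to use in deciding how much early testing needs people with a stoma.

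**Working it through.** The plan gives no figure to reproduce here. The check compares the texts and then scales the possible effect.

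**Step 1: scope of the topical-steroid exclusion against the sites tested.**

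| | Sites tested | Topical steroid barred on | Skin named in justification |
|---|---|---|---|
| Part A | Abdominal | Abdominal | Abdominal |
| Part B | Peristomal and abdominal | Peristomal only | Peristomal only |

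Part A's row is consistent. In Part B the abdominal site has no topical restriction. The peristomal wording cannot be stretched to cover it, because section 3 treats the two as distinct skin types.

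**Step 2: does anything else close the gap?**

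- Inclusion 5 and exclusion 4 cover the abdominal test area, but they concern the state of the skin, not steroid exposure. Skin that looks normal during or after treatment passes both.
- The systemic steroid exclusion does not reach topical use.
- Section 6.2.8 bars only lotion, and only after pre-stripping.
- Table 1 repeats the eligibility check at visits 1-25, and section 6.1.7 requires withdrawal when a criterion is no longer met. Both act only on the criteria as written, so abdominal topical steroid started between visits triggers neither if the skin passes assessment.
- Section 6.2.1 schedules skin measurements under each strip area before application. These allow change from baseline, but the water-loss and hydration objective compares the sites themselves, so a site already altered at baseline remains altered in that comparison.

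A subject who stopped an abdominal steroid cream two weeks ago and now has clear, intact skin is not barred by that use. The same cream used beside the stoma would exclude that subject.

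**Step 3: scale.**

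Inputs:

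- n, the number of subjects: at least 4 per cohort and up to 50 in Part B (section 7.2). Eight is an illustrative intermediate size.
- k, the number of subjects with recent topical steroid on the abdominal test area: not in the documents.
- d, the steroid effect on such a subject's abdominal reading for a given endpoint: not in the documents, and taken as equal across exposed subjects.

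Let the site difference for each subject be peristomal minus abdominal. An exposed subject's difference changes by −d, and the others do not change. The mean difference therefore shifts by −(k × d)/n. In absolute size:

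| n | k | Shift |
|---|---|---|
| any | 0 | 0 |
| 4 | 1 | d/4 = 0.25d |
| 4 | 2 | 2d/4 = 0.50d |
| 8 | 1 | d/8 = 0.125d |
| 50 (all Part B pooled) | 1 | d/50 = 0.02d |

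**The case against.** **The eligible group is narrow.** Systemic steroid is excluded whatever the site, and inclusion 5 and exclusion 4 should remove many people with active abdominal skin disease. This stands: what remains is mainly recent topical use on skin that looks normal at assessment. It shrinks the gap without closing it.

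**Little formal inference is at risk.** The affected objectives are secondary and exploratory, section 7.4 sets no success criteria, and sections 7.1 and 7.3 rely primarily on summary statistics. The primary objective, water absorption of the adhesives, is not a comparison of skin sites and is not challenged here. This also stands, and it limits the harm to interpretation.

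**The arithmetic is generic.** Any unusual subject carries a quarter of a mean of four. That is fair, and four is the smallest cohort allowed. The pooled figure of 0.02d belongs beside it, since section 7.1 foresees a joint evaluation. Even so, section 7.1 bases that evaluation primarily on cohort summaries, so the small-cohort figures remain relevant.

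**Stronger readings that the documents do not support.** A reader might infer that the comparison is biased. That requires exposed subjects to enrol and an effect that matters, and the documents establish neither. A reader might infer that every steroid effect falls on the abdominal side. Topical use before the one-month window is allowed at both sites, so only recent exposure is treated unequally. A reader might also infer that the effect could not be detected. Section 7.1 provides for listings as well as summaries, so an aberrant reading in a cohort of four would probably be seen, although its cause might not be.

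**Conclusion.** The gap in the text is certain: it appears in the synopsis, in section 6.1.5 and in the justification, and no other provision closes it. The bias is possible, not demonstrated. It depends on subjects with recent topical steroid on the abdominal test area taking part, and on d being non-negligible for the endpoint concerned.

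On those assumptions, one exposed subject moves the mean site difference by between 0.02d (all 50 pooled) and 0.25d (a cohort of four). Water loss and hydration are the most directly exposed, since those readings are themselves the comparison. The size cannot be put in measured units from the documents. The consequence is limited to exploratory secondary objectives, but the correction is cheap enough to make.

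**What to change.** Reconcile Part B exclusion 2 with the Part B test sites, in both the synopsis and section 6.1.5. Extend the topical-steroid restriction to the skin tested in Part B, naming both peristomal and abdominal, and keep the existing one-month window and the systemic clause as they are. This gives exclusion 2 the same reach as inclusion 5 and exclusion 4. Amend the Part B justification so that it names abdominal as well as peristomal skin. The eligibility checks already in Table 1 can apply the wider criterion without a new procedure.

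**Cost.** A few words in two places plus the justification, handled as an amendment under section 9. There may be a few more screen failures. Because section 6.1.7 requires withdrawal when a criterion ceases to be met, a subject who starts topical steroid on the abdominal test area between visits would also have to be withdrawn. The documents give no basis for estimating either number.
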